#### 9.7.6 Analysis of safety data

Patients who took at least one dose of Betaferon® and provide sufficient information whether they had an adverse event or not (i.e. who have a follow-up visit page and/or an adverse event page) will be eligible for safety analysis (safety analysis set). The full analysis set (FAS) will include all patients who have data available at baseline as well as at least from one post-baseline visit.

Adverse events will be summarized using the MedDRA coding system. Event rates for single adverse events will be calculated based on the total number of patients valid for safety analysis. Adverse events will be categorized according to relation, seriousness, discontinuation of therapy, action taken and outcome. Special attention will be paid to serious adverse events and unexpected or unlisted ADRs.

Category counts and frequencies (percentages) will be calculated for overall tolerability.

All patients will be presented with all details from the AE report form.

Device events will be summarized using the MedDRA coding system. Event rates for device events will be calculated based on the total number of patients valid for safety analysis.

Further details of the safety analysis are described in the SAP.

## 9.7.7 Bias, confounding and effect-modifying factors

In general data collected in this study may suffer from biases (e.g. interviewer bias, either by systematic differences in data recording or different interpretation of information on exposure or outcome for different patients, reporting as well as selection bias). Information bias with respect to

injection data will be avoided since the autoinjector automatically records injection related data; however information obtained from patients may suffer from recall bias, which is inherent to the study design. Further, prospective studies are prone to bias from loss to follow-up or change in methods over time. To decrease reporting bias source data verification will be performed in at least 10% of the sites. Sites will be selected according to several criteria, main criteria for site selection will be: availability of suitable patients and an equal geographical distribution. Patients should be enrolled consecutively. Investigators should select patients to be documented in the study only based on eligibility according to inclusion and exclusion criteria. No further selection should be applied. However, sites agreeing to participate in the study may not be equally distributed across Germany; hence, patients enrolled may not be representative of all German MS patients.

Primary and secondary outcome variables will be analyzed with regard to different baseline factors. However, unknown and unmeasured risk factors for the outcome variables will exist and might lead to confounding when comparing results in different subgroups and when comparing study results with historical results from clinical studies.

For the secondary objectives we will also evaluate post-baseline variables with respect to adherence. Potential bias may arise from reciprocal influence of these variables on each other during the study course, requiring extreme caution when interpreting these results.

Both BETACONNECTTM-naïve and BETACONNECTTM-experienced patients will be included in the study. Regarding experienced patients it needs to be considered that this group of patients may be "positively selected" with respect to adverse effects, i.e. they may still be using the device because they experience no or only mild adverse effects. We will address this by performing stratified analyses in the naïve and experienced groups in addition to the overall group and also investigate for interaction by adding an interaction term between the variables "previous usage of BETACONNECTTM" and "compliance/adherence" to the multivariable-adjusted models.

The consideration of treatment-naïve and -experienced patients with respect to usage of the device (BETACONNECTTM) as well as with respect to usage of the drug (Betaferon®) also leads to another aspect: patients experiencing injection-related adverse effects like skin reactions (in the past and during course of study) may differ from those not experiencing adverse effects with respect to adherence (non-adherent patients may not be exposed to risk of skin reactions, while on the other hand, skin reaction may induce non-adherence). One way to address this potential "reverse causation" bias is to group study participants according to their experience with the device or the drug. Hence, by performing separate analyses as described in the previous paragraph we will also be able to appreciate "reverse causation".

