# Enrollment / Initial visit

Once a patient is found eligible for inclusion, the investigator will inform the patient about the study. Where applicable, this will include discussing the consent form and asking the patient to read and - when agreeing to participate - sign the informed consent.

Typical information to be collected at the baseline visit includes:

- Date of visit
- Date of birth (at least year)
- Sex (female, male)
- Race / ethnicity (Caucasian, asian, black, other)
- Height (cm)
- Weight (kg)
- Smoking (current, past, never)
- Employment status (employed, retired, keeping house, student, seeking work, self-employed, other, not reported)
- Education level (elementary education, secondary education, college or university education, not reported)
- Marital status (married/partnership, single)
- Medical history
  - Concomitant diseases
  - Concomitant medication
    - Trade name or INN
    - Start date (at least year)
    - Stop date or "continued"
    - Daily dose, if applicable
    - Indication
- Intake of vitamin D supplements (yes vs. no; if yes which dosage?)
- Intake of other nutrients or vitamins (yes vs. no)

IMPACT number 18016; BETAPREDICT; Version 1.0, 12 February 2015

- Specific MS history
  - Date of first clinical event suggestive of MS (DD/MM/YYYY)
  - Date of initial diagnosis (DD/MM/YYY)
  - diagnostic criteria
    - o according to McDonald criteria
    - o according to Poser criteria (CDMS)
  - Number of further demyelinating events/relapses (number during past 2 years)
    - If number >0: date of onset (DD/MM/YYYY), ongoing
  - Concomitant diseases of special interest
    - Depression
    - o Anxiety
    - o Fatigue
  - Betaferon® administration record
    - Betaferon® treatment (ongoing/naive)
    - Date of first Betaferon® injection (DD/MM/YYYY)
  - Current application form for Betaferon® (prior to study)
    - Manual injection (yes/no)
    - Use of auto-injection device (yes/no)
      - If Yes, please tick (BETACONNECTTM, BETACOMFORT®, BETAJECT Comfort®, BETAJECT lite®, other)
  - Treatment days with Betaferon® during last month
    - Number of expected treatment days
    - Number of true treatment days
    - o N/A
  - Participation in the BETAPLUS® nurse support program (yes/no)
  - Participation in the PTMS program (yes/no)

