#### 9.7.4 Analysis of primary outcome(s)

Our primary analysis will be after 12 and 24 months of observation; however, we will also perform analyses for the visits in between.

For the analyses of our primary outcome compliance we will use descriptive statistics to characterize compliance (in percent) by calculating mean ( $\pm$ SD), median, min, and max. This will include a stratified analysis according to the patients' pre-study experience with the BETACONNECTTM, i.e. new patients vs. experienced patients.

We will then investigate the association between baseline covariates and compliance in percentage using Analysis of Variance (ANOVA) and linear regression. First, we will use ANOVA to investigate mean differences in compliance for each of the categorical covariates. Second, we will use linear regression with compliance as the dependent variable and each of the covariates as independent variables. We will investigate univariate associations and then build a multivariable-adjusted model accounting for all covariates. With respect to the ANOVA analysis we will chose covariates as potential predictors that show a univariate association in the overall comparison using the F-test with a  $p \le 0.1$  and further investigate those in pairwise comparisons using both univariate and multivariable models. Finally, employing linear regression models, we will use a stepwise selection procedure to determine predictors of compliance, considering all covariates as potential predictors.

For the analyses of our co-primary endpoints we will likewise use descriptive statistics to characterize persistence and overall adherence (yes, no) using category counts and frequencies (percentages). This will include stratified analyses according to the patients' pre-study experience with the IMPACT number 18016; BETAPREDICT; Version 1.0, 12 February 2015 Page 42 of 75

BETACONNECTTM, i.e. new patients vs. experienced patients. In further analyses we will use logistic regression to investigate the association between baseline covariates as the independent variables and persistence and overall adherence as the dependent variables. The regression analyses will include investigating univariate associations, multivariable-adjusted associations, and finally as stepwise selection procedure to determine predictors of persistence and overall adherence, similar to the analysis of the endpoint compliance.

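### The planned interaction term puts the outcome among the regressors, so it cannot test whether predictors differ by device experience

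*Protocol*

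**What the plan says.** Protocol Section 9.7.7 notes that patients already using BETACONNECT may be a favourable selection, because those who tolerated it poorly may have stopped. It plans two responses. One is stratified analysis in device-naive and device-experienced patients alongside the overall group. The other is to "also investigate for interaction by adding an interaction term between the variables" previous usage of BETACONNECT "and 'compliance/adherence' to the multivariable-adjusted models".

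Section 9.7.4 defines the models. For the primary endpoint it is "linear regression with compliance as the dependent variable and each of the covariates as independent variables". For the co-primary endpoints it is logistic regression with "persistence and overall adherence as the dependent variables". The same section stratifies the descriptive analyses by "pre-study experience with the BETACONNECT" autoinjector and, numbers permitting, repeats the predictor analyses in the two device groups.

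Section 9.7.7 then turns to reverse causation between injection-related adverse effects and adherence. It says that one remedy is to "group study participants according to their experience with the device or the drug", and that the separate analyses of its preceding paragraph provide this. Those analyses are by device only.

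**The concern.** An interaction test for effect modification multiplies the suspected modifier by a predictor and leaves the outcome on the left-hand side. Here the modifier is multiplied by the outcome, and no predictor is named. The protocol specifies both factors and the target models, so this is a stated rule and not a detail left to the statistical analysis plan.

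The study exists to find baseline predictors in a cohort that mixes naive and experienced patients. Whether a predictor works alike in both groups is a question readers will ask. Run as written, the formal answer would be a very strong apparent interaction for compliance and a model that does not converge properly for the two binary endpoints, whatever the truth.

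**Working it through.** **Inputs from the protocol.** The interaction factors and target models come from Section 9.7.7, and the dependent variables from Section 9.7.4. The 7-point difference, SD of 10%, 5:2:1 group ratio, alpha of 0.05, 80% power, 200 analysable patients and 20% missing data come from Section 9.5.

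**Assumed for the simulation.** Mean compliance 90, one standard-normal baseline predictor with slope 2, experienced share 0.2, 0.5 or 0.8, 2,000 data sets per scenario.

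**The plan's own figure.** The plan gives no figure for the interaction, so its sample size only sets N. At N = 200 and 5:2:1, the two smaller groups have 50 and 25 patients. The noncentrality is 7 / (10 × √(1/50 + 1/25)) = 7 / 2.449 = 2.858, and the noncentral t gives power 0.812 (N = 192 gives 0.796). Then 200 / (1 − 0.20) = 250. The stated size is reproduced and is not in question.

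**Algebra.** Let Y be compliance, E = 1 for device-experienced and 0 for device-naive, and X a baseline predictor. As written the model is

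Y = a + bE + cX + d(E × Y) + error.

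For E = 1 the product equals Y, so d = 1, b = −a and c = 0 fit those patients exactly. For E = 0 the product is zero and does nothing. The estimate of d is drawn to 1 whatever the distribution of Y. R-squared then largely reflects the share of experienced patients. If compliance were also entered as a main effect, the fit would be perfect and every predictor coefficient would vanish.

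**Simulation, linear model.** E × Y is the term as written; E × X is a well-formed term.

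| Experienced share | Truth | E × Y rejects | E × Y coefficient | R-squared | E × X rejects |
|---|---|---|---|---|---|
| 0.2 | no device effect | 100% | 0.968 | 0.229 | 4.9% |
| 0.2 | device main effect of 5 points | 100% | 0.968 | 0.258 | 4.7% |
| 0.2 | slope differs by 4 points per SD | 100% | 0.926 | 0.273 | 57.2% |
| 0.5 | no device effect | 100% | 0.980 | 0.514 | 5.2% |
| 0.5 | device main effect of 5 points | 100% | 0.980 | 0.545 | 5.3% |
| 0.5 | slope differs by 4 points per SD | 100% | 0.949 | 0.581 | 79.0% |
| 0.8 | no device effect | 100% | 0.993 | 0.809 | 4.4% |
| 0.8 | device main effect of 5 points | 100% | 0.993 | 0.815 | 4.8% |
| 0.8 | slope differs by 4 points per SD | 100% | 0.978 | 0.843 | 59.4% |

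The term as written rejects equally often with and without modification. The well-formed term holds its nominal 5% and responds to real modification.

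**Logistic models.** For a binary outcome, E × Y = 1 implies Y = 1. In one simulated data set of 200, the product-equals-1 row held 0 non-adherent and 70 adherent patients, and the product-equals-0 row held 55 and 75. The empty cell is quasi-complete separation, so the maximum-likelihood estimate for the term is not finite.

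**Power of a well-formed term for compliance.** For two binary factors with proportions p and q, the standard error of the difference in differences is 10 / √(200 × p(1−p) × q(1−q)). Power for 7 points is Φ(7/SE − 1.96), and the effect detectable with 80% power is (1.96 + 0.8416) × SE.

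| p, q | SE | Power for 7 points | Detectable effect |
|---|---|---|---|
| 0.5, 0.5 | 10/√12.5 = 2.83 | 70% | 7.9 points |
| 0.2, 0.5 | 10/√8 = 3.54 | 51% | 9.9 points |
| 0.2, 0.2 | 10/√5.12 = 4.42 | 35% | 12.4 points |

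**The case against.** Three arguments weigh on the other side.

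*The term may be meant loosely or for other models.* It would be well formed where adherence is a regressor, for instance in a model of relapses or EDSS change. But Section 9.7.7 refers to the multivariable-adjusted models, and only Section 9.7.4 describes such models. The regressions in Section 9.7.5 have PTMS participation as regressor and adherence among the outcomes. If interaction with regard to compliance was meant, no predictor is named. The wording needs correction on either reading.

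*The bias handling does not rest on this term.* This stands. A reader might infer that the study has no working safeguard against selection. The documents do not support that: the device strata are a separate analysis, are untouched by the faulty term, and address the selection that Section 9.7.7 actually describes, namely among device-experienced patients. Comparing predictor estimates between strata can show differences descriptively.

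*Drug history is not ignored.* This also stands in part. Section 9.7.4 lists new versus existing Betaferon treatment among the candidate predictors, and Section 9.7.1 allows stratification by baseline characteristics. Section 9.7.7 offers grouping by device or drug as one possible remedy, not as a requirement. What remains is narrower: no drug-history stratum or interaction is named, although a long-term Betaferon user new to the device counts as device-naive. A reader might want to put a size on that mixing. The documents give neither the mix nor stopping rates by drug history. Section 7 also expects almost all Betaferon patients in Germany to be using the device by mid-2015, early in a recruitment period running to Q4 2016. No figure is therefore justified, nor is a claim that drug history must be the main stratifier.

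**Conclusion.** The interaction term is wrong as written. For compliance it is significant by construction (100% of data sets in all nine scenarios, coefficient 0.93 to 0.99). For persistence and overall adherence it is not estimable. This follows from the algebra and does not depend on the assumed mean, slope or device share, which affect only the illustrative numbers.

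The damage is confined to that test. The analyses are declared exploratory and descriptive, and the endpoints, sample size and models without the term are unaffected. It would go too far to say that the predictor analysis as a whole is invalid or that selection cannot be examined at all. The mismatch between the drug-or-device statement and the device-only strata is a secondary point.

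**What to change.** In Section 9.7.7, and correspondingly in the statistical analysis plan, replace the term with interactions between previous BETACONNECT use and a short list of key baseline predictors. Fix the list before the 12-month analysis. Compliance, persistence and overall adherence should appear only as outcomes. Label these tests exploratory, report estimates with confidence intervals, and state the limited power given above, which applies to compliance with 200 analysable patients. A non-significant result should not be read as showing that predictors work alike in both groups.

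As a secondary suggestion, either add a supplementary analysis stratified by Betaferon-naive versus ongoing treatment, or limit the reverse-causation statement to device experience. Treatment status and the date of first injection are already recorded at the initial visit.

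The cost is about one paragraph of wording and no new data. The downside is a few more low-powered exploratory tests, which is why the list should be short.

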# 9.8 Quality control

#### 9.8.1 Data quality

Before study start at the sites, all investigators will be sufficiently trained on the background and objectives of the study and ethical as well as regulatory obligations. Investigators will have the chance to discuss and develop a common understanding of the study protocol and the CRF.

A CRO will be selected and assigned for EDC system development, quality control, verification of the data collection, data analysis and data transfer to Bayer. All results will be verified by an independent data analyst at the selected CRO.

All outcome variables and covariates will be recorded in a standardized CRF. After data entry, missing or implausible data will be queried and the data will be validated. A check for multiple documented patients will be done.

Detailed information on checks for completeness, accuracy, plausibility and validity are given in the Data Management Plan (DMP). The same plan will specify measures for handling of missing data and permissible clarifications. The DMP is available upon request (see BF1502\_DMP\_final\_yyyymmdd Table 2: List of stand-alone documents, Annex 1).

National and international data protection laws as well as regulations on observational studies will be followed. Electronic records used for capturing patient documentation (eCRF) will be validated according to 21 Code of Federal Regulations (CFR) Part 11 (FDA). The documentation is available upon request (see BF1502\_EDC\_system validation\_final\_yyyymmdd>, Table 2: List of stand-alone documents, Annex 1).

#### 9.8.2 Quality review

In a subset of patients (at least 10% of all patients) source data verification will be conducted. The purpose is to review the documented data for completeness and plausibility, adherence to the study protocol and verification with source documents. To accomplish this, monitors will access medical records on site for data verification. Detailed measures for quality reviews will be described in the Quality Review Plan (QRP). The QRP is available upon request (see BF1502\_QRP\_final\_yyyymmdd Table 2: List of stand-alone documents, Annex 1).

#### 9.8.3 Storage of records and archiving

The sponsor will make sure that all relevant documents of this non-interventional study including CRFs and other patient records will be stored after end or discontinuation of the study for at least 10 years. Other instructions for storage of medical records will remain unaffected.

The investigators participating in the study have to archive documents at their sites according to local requirements, considering possible audits and inspections from the sponsor and/or local authorities. It is recommended to also store documents for a retention period of at least 10 years.

## 9.8.4 Certification/qualification of external parties

N/A

## 9.9 Limitations of the research methods

This prospective observational cohort study provides the opportunity to collect data of real-life treatment adherence that can be analyzed and disseminated in a timely manner. However, this study is a single arm cohort study without a comparison group. Thus, in addition to subgroup analyses within this study, the results can only be compared with historical data from other studies. Such a comparison is prone to bias and confounding as historical data may differ by method of ascertainment and the data ascertained in our study may not be available.

In general caution needs to be exercised when investigating associations between variables collected in observational studies, since they may be spurious and generated by study inherent biases. Hence, any association identified needs to be carefully examined with respect to causality, i.e. if certain criteria for causality apply (e.g. criteria by Bradford Hill).

#### 9.10 Other aspects

N/A

# **10** Protection of human subjects

#### 10.1 Ethical conduct of the study

This study is an observational study where Betaferon is prescribed in the customary manner in accordance with the terms of the marketing authorization. There is no assignment of a patient to a particular therapeutic strategy. The treatment decision falls within current practice and the prescription of the medicines is clearly separated from the decision to include the patient in the study. No additional diagnostic or monitoring process is required for participation or during the study. Epidemiological methods will be used for the analysis of the collected data.

#### **10.2** Regulatory authority approvals/authorizations

The study will be carried out within an approved indication in accordance with guidelines and regulations of EMA, FDA and applicable local law(s) and regulation(s) (e.g. Regulation (EU) No 520/2012). Recommendations given by other organizations will be followed as well (e.g. EFPIA, ENCePP). ICH-GCP guidelines will be followed whenever possible.

## 10.3 Independent ethics committee (IEC) or institutional review board (IRB)

Documented approval from appropriate IECs/IRBs will be obtained for all participating sites prior to study start. When necessary, an extension, amendment or renewal of the IEC / IRB approval must be obtained and also forwarded to the sponsor. The IEC / IRB must supply to the sponsor, upon request, a list of the IEC/IRB members involved in the vote and a statement to confirm that the IEC / IRB is organized and operates according to applicable laws and regulations.

